7.1.8 Medical History

Events reported on the medical history page of the eCRF at the Screening visit will be coded according to MedDRA[®]. The number and percentage of subjects having each system organ class (SOC) and preferred term will be summarized by treatment group and overall.

7.1.9 Psychotherapy

A listing of CRF collected psychotherapy will be provided for all safety subjects.

7.2 Efficacy

The primary efficacy analysis will be performed based on the ITT population ([Section 6.1.7](#)). Assessment of the primary efficacy endpoint on the PP population will be conducted as supportive analyses.

7.2.1 Analysis Specifications

7.2.1.1 Level of Significance

Unless otherwise specified, all statistical tests will be interpreted at a 2-sided significance level of 5% and all confidence intervals (CIs) will be presented at a 2-sided confidence level of 95%.

The overall type I error rate for testing dasotraline 6 mg/day group versus placebo and dasotraline 4 mg/day group versus placebo will be strongly controlled at the 5% level across the primary endpoint and key secondary endpoints, which is detailed in [Section 6.2.5](#).

7.2.2 Presentation of Analysis Result from Statistical Model

Whenever MMRM or ANCOVA analysis are conducted, LS mean of treatment differences, associated 95% CIs and p-values (raw) will be generated per corresponding statistical model. For each efficacy variable, effect sizes for within-group and between-group are presented at each post-baseline visit using a same approach in [Section 7.2.3.2.1](#).

7.2.3 Primary Efficacy Endpoint

7.2.3.1 Definition

The primary efficacy endpoint is the change from baseline in the number of binge days per week at Week 12. See [Section 5.1.1](#) for details of data definition and derivation at each assessed time point.

7.2.3.2 Analysis Methods

7.2.3.2.1 Primary Efficacy Analysis

The primary efficacy analyses of primary efficacy endpoint (the change from baseline in the number of binge days per week at Week 12) will be performed using a likelihood-based mixed model for repeated measures (MMRM). The response (dependent) variable is the change from baseline in the number of binge days per week assessed at Weeks 1, 2, 3, 4, 6, 8, 10, and 12. Specifically, the MMRM model includes fixed effects terms for treatment, visit (as a categorical variable), pooled center, baseline binge days category (stratification factor), the number of binge days per week at baseline, and treatment-by-visit interaction. Restricted maximum likelihood estimation method will be applied using unstructured covariance model. The Kenward Roger approximation will be used to estimate denominator degrees of freedom. In case of a failure of convergence with the unstructured covariance, the following structures may be assessed in a sequential order: heterogeneous Toeplitz, Toeplitz, and spatial exponential covariance pattern model. Of the above 3 covariance structures, the first covariance structure yielding convergence in the MMRM model will be used for the MMRM analysis. The spatial exponential model is selected for the analysis of data with unequally spaced time points. The LS mean treatment differences (each dasotraline group minus placebo group) of change from baseline at Week 12, their 2-sided 95% CIs, and the associated p-values will be calculated based on this model. At each post-baseline visit, effect size for within-group and between-group will be presented. Within-group effect size is calculated as mean change from baseline divided by the SD. Based on the MMRM, between-group effect size at a visit is calculated as the LS mean difference from placebo divided by the model estimate of the pooled SD at the visit, which is obtained from the square root of the diagonal element, associated at the visit, from the covariance matrix.

In addition, descriptive statistics (mean, SD, 95% CI) will be provided for the number of binge days per week and change from baseline by study visit for each treatment group. The likelihood based mixed effects model can accommodate incomplete data under the assumption of ignorable attrition.

The primary efficacy analysis will be repeated for the PP population to examine the impact of premature dropouts and/or protocol deviations.

7.2.3.2.2 Assessment of Model Assumptions in the Primary Efficacy Analysis

The normality and homoscedasticity assumptions underlying the primary MMRM model will be assessed graphically. Conditional studentized and scaled residuals will be plotted against the predicted values, respectively, and Q-Q (quantile-quantile) plots of these residuals versus the expected quantiles of the standard normal distribution will be presented to provide a graphical view of similarity and difference in the two distributions. Cumulative distribution function (CDF) of the primary endpoint will be also provided by treatment group. Considering that the validity of likelihood-based analyses also hinge on correct specification of the correlation

structure, an unstructured correlation matrix for modelling the within-patient errors is used (see [Section 7.2.3.2.1](#)) as a means of avoiding misspecification. However, this approach does not guarantee validity. If unstructured fails to converge, a more parsimonious model is likely necessary, but not necessarily correct; for such case, MMRM based on structures more general than unstructured one, ie, separate unstructured matrices by treatment, will be checked.

If there are evidences of deviations from the model assumption(s), the degree and nature of such deviation(s) will be explored to better understand the potential impact on interpretation of the primary efficacy analysis.

7.2.3.2.3 Supportive Analysis

The primary efficacy endpoint will be analyzed using an analysis of covariance (ANCOVA) model and the LOCF approach, as a supportive analysis. The model include terms for treatment, pooled center, and baseline binge days category (stratification factor) as factors, and the number of binge days per week at baseline as covariates. The LS mean of treatment differences (each dasotraline group minus placebo group), their 2-sided 95% CIs, and the associated p-values will be obtained from the model.

Effect sizes for within-group and between-group will be presented at each post-baseline visit. Within-group effect size is calculated as mean change from baseline divided by the SD. Based on the ANCOVA model, between-group effect size is calculated as the LS mean difference from placebo divided by the model estimate of the pooled SD, which is calculated as the SE of the LS mean difference divided by the square root of the sum of inverse treatment group sizes.

7.2.3.2.4 Sensitivity Analyses

To address early dropouts under the assumption of missing not at random (MNAR), a pattern-mixture model (PMM) using a placebo-based multiple imputation method ([Attachment 9.3.1](#)) and a pattern mixture model using multiple imputations with penalties (ie, tipping point analysis by deflating the individually estimated treatment effect size by known factors) ([Attachment 9.3.2](#)) will be performed as sensitivity analyses to explore the robustness of the MMRM results for the primary analysis based on the ITT population.

The PMM using a placebo-based multiple imputation method is a method based on methodology proposed by Ratitch and O’Kelly ([\[5\]](#)). The assumption that efficacy profiles of dropouts after discontinuation are similar to those of placebo subjects is considered very conservative because this methodology tends to minimize the difference between each dasotraline group and placebo group.

The PMM using multiple imputations with penalties by deflating the individually estimated treatment effect size by known factors provides a way to assess plausible deviations from MAR [\[8\]](#). The tipping point, which is defined as the value of the factor where statistical significance of

321

treatment effect is lost, will be evaluated. If the tipping point is unrealistically high, treatment effect is robust. This approach will generate a serial of conservative estimates and provide the extent of robustness of primary efficacy result in a stepwise way.

In case of a deviation from the assumptions required for the primary analysis ([Section 7.2.3.2.2](#)), to confirm the robustness of the primary analysis result, two additional sensitivity analyses, permutation test and Generalized Linear Mixed Model (GLMM) analysis ([Attachment 9.3.3](#)) will be performed.

Permutation test is to fit a large number of datasets (ie, 10000) based on a same MMRM for the primary analysis with randomly assigning pseudo-treatment group designations. The empirical p -value will be obtained from the permutation test. The non-parametric based permutation test provides a conservative way to assess the primary efficacy endpoint.

GLMM analysis will fit count data over time (ie, number of binge days among number of assessed days at each visit period) based on a binomial distribution. This approach may better address the potential unequal variances assumption among subjects due to different number of assessed days (either because of assessment schedule, early dropout, or missing diary) among subjects and therefore is expected to better reflect the true distribution of the primary efficacy endpoint.

7.2.3.2.5 Exploratory Analyses Related to Planned Region and Actual Region Group

For primary efficacy variable, following exploratory analyses will be performed using the same predictor terms as described above (Sections 7.2.3.2.1, 7.2.3.2.3, and 7.2.3.2.4) by replacing the fixed term ‘pooled center’ with either the planned region or actual region group (pooled ones when applicable), respectively, to evaluate the impact of mis-stratification of region on treatment effect and further corroborate the primary efficacy result.

- the MMRM model,
- the ANCOVA model
- the PMM using a placebo-based multiple imputation method,
- the PMM using multiple imputations with penalties by deflating treatment effect size,

7.2.3.2.6 Assessment of Dropout and Dropout Profiles

To assess the impact of the drop-outs on the primary efficacy variable, a plot of cumulative distribution of the primary efficacy endpoint (change from baseline in number of binge days per week at Week 12) will be presented by treatment using the worst imputation for dropouts (i.e., missing value at a visit will be imputed by the most extreme increase in binge days at the visit per treatment group).

321

Subjects will be grouped by the visit group at which they have their last number of binge days per week. This will result in five categories for subjects discontinuing: Weeks 1/2 dropouts, Weeks 3/4 dropouts, Weeks 6/8 dropouts, Weeks 10/12 dropouts, and Completers. Specifically, for an example, subjects who discontinue after Week 2 visit but prior to or at Week 4 visit will be classified as Weeks 3/4 dropouts. The means change from baseline in number of binge days per week and BE-CGI-S score over time will be plotted by dropout category for each treatment (prior to and including the termination visit).

A similar plot will be generated using the grouped termination reasons defined in [Table 7](#) as below. Summaries involving dropout category and termination reason will be based on the ITT population. The reason of withdrawal by subject will be reviewed prior to DBL to better understand the sub-category it belongs (due to efficacy, due to adverse reaction, due to other).

Table 7 Reasons for Discontinuation and Mapping for Termination Reason

eCRF Term	Grouped Term
Adverse event	Adverse event
Lack of efficacy	Lack of efficacy
Lost to follow-up	Lost to follow-up or withdrew consent
Withdrawal by subject	
Non-compliance with study drug	Non-compliance and other
Protocol Violation	
Pregnancy	
Other	

7.2.3.2.7 Missingness of Diary Entry

Summary statistics (ie, N, mean, median, range) of number of days with missing diary entries and missing diary rate (calculated as 100*the number of days with missing diary divided by the total number of days in the assessed visit period), as well as number and percentage of subjects of each missing entries category (ie, missing 1 days only, 2 days only, 3 days only, 4 days only, and >4 days) will be summarized by visit and overall DB treatment period for each treatment. A listing of missing diary entry by subject will be provided as well.

7.2.4 Key Secondary Endpoints Analyses

7.2.4.1 Definition

The key secondary efficacy endpoints involved in the hypothesis testing of each dasotraline dose (4 mg/day and 6 mg/day) versus placebo include change from baseline at Week 12 in BE-CGI-S score and Y-BOCS-BE total score, and percent of subjects with a 4-week cessation from binge eating prior to Week 12/EOT. See [Section 5.1.1.4](#) for details.

7.2.4.2 Analysis Methods

Change in BE-CGI-S score and Y-BOCS-BE total score

Continuous key secondary variables (ie, change in BE-CGI-S score and Y-BOCS-BE total score) will be analyzed with an MMRM model similar to the primary efficacy analysis ([Section 7.2.3.2.1](#)) by adjusting the corresponding baseline. The LS mean treatment differences (each dasotraline group minus placebo group) of change from baseline at Week 12, their 2-sided 95% CIs, and the associated p-values will be calculated based on the model. Effect sizes for within-group and between-group will be presented at each post-baseline visit using a same approach in [Section 7.2.3.2.1](#).

As a supportive analysis of the above MMRM analyses, the change from baseline in BE-CGI-S and Y-BOCS-BE total score at Week 12 will be analyzed using an ANCOVA model and the LOCF approach for the ITT population, which includes terms for treatment, pooled center, baseline binge days category (stratification factor), and corresponding baseline score as covariate; Effect sizes for within-group and between-group will be presented at each post-baseline visit by a similar approach described in [Section 7.2.3.2.3](#).

To address early dropouts or potential deviation from the model assumption(s), sensitivity analyses similar to [Section 7.2.3.2.4](#), including PMM using a placebo-based multiple imputation method, PMM using multiple imputations with penalties by deflating the individually estimated treatment effect size, and permutation test may be conducted for the key secondary endpoint for BE-CGI-S; PMM using a placebo-based multiple imputation method may be conducted for Y-BOCS-BE total score.

For above key secondary efficacy variables, following exploratory analyses will be performed using the same predictor terms described above by replacing the fixed term ‘pooled center’ with the planned region or actual region group (pooled one when applicable), respectively, to evaluate the impact of mis-stratification of region on treatment effect and further corroborate these key secondary efficacy result.

- the MMRM model
- the PMM using a placebo-based multiple imputation method
- the PMM using multiple imputations with penalties by deflating treatment effect size (for BE-CGI-S only)

Percent of subjects with a 4-week cessation from binge eating

The categorical key secondary efficacy endpoint of percent of subjects with a 4-week cessation from binge eating will be analyzed using a logistic regression model with treatment, baseline binge days category (stratification factor), and baseline number of binge days per week as covariate using a LOCF approach based on ITT population. The odds ratios, their 2-sided 95%

321

CI, and the associated p-values for each dasotraline group over the placebo group will be derived from the model.

As a supportive analysis, percent of subjects with a 4-week cessation from binge eating will be analyzed by an inverse probability weighting (IPW) model; See [Attachment 9.3.4](#) for details about IPW method ([6]). A sensitivity analysis per quasi-likelihood approach will be conducted by fitting same fixed terms as listed above with random-residual based on binary distribution with logit link, which will effectively lift the constraints of the model parameter. The above approach will be implemented using GLIMMIX procedure in SAS.

For above logistic regression model, two exploratory analyses will be performed using same predictor terms with an additional fixed term of planned or actual region group (pooled one when applicable), respectively, to evaluate the impact of mis-stratification of region on treatment effect and further corroborate key secondary efficacy results.

7.2.5 Multiplicity Adjustment

To control the overall type I error rate strongly at 5% for the primary and key secondary endpoints, for the hypotheses to be tested, a sequential testing strategy will be used. Following the fixed sequence closed testing procedure in [Figure 1](#), testing will only proceed conditional on the statistical significance of the test(s) of prior level(s) at a 2-sided 5% significance level. See [Section 6.2.5](#) for details.

7.2.6 Other Secondary Endpoints Analyses

7.2.6.1 Definition

The other secondary endpoints of interest are:

- Change from baseline in number of binge days per week at Weeks 1, 2, 3, 4, 6, 8, and 10
- Change from baseline in number of binge episodes per week at Weeks 1, 2, 3, 4, 6, 8, 10, and 12
- Change from baseline in BE-CGI-S score at Weeks 2, 4, 6, 8, and 10
- Change from baseline in Y-BOCS-BE total score at Weeks 2, 4, 6, 8, and 10 and subscale scores (obsessions and compulsions) at Weeks 2, 4, 6, 8, 10, and 12
- Change from baseline in MADRS total score at Week 12
- Change from baseline in HAM-A total score at Week 12
- Change from baseline in SDS total score and subscale scores (school/work disability, social life disability, and family life disability) at Weeks 6 and 12
- Proportion of binge eating responders (ie, $\geq 75\%$ reduction in the number of binge eating episodes) at Week 12

321

- Change from baseline in EDE-Q modified including EDE-Q modified global score and 3 subscale scores (dietary restraint, shape/weight overvaluation, and body dissatisfaction) at Week 12

7.2.6.2 Analysis Methods

The analyses of continuous variables associated with the primary efficacy endpoint and the key secondary endpoints (ie, the change from baseline in number of binge days per week, BE-CGI-S score and Y-BOCS-BE total score) have been described on [Sections 7.2.3](#) and [7.2.4](#) of this SAP.

Continuous variables related to change in number of binge episodes per week, Y-BOCS-BE subscale scores, and SDS-total score and subscale scores will be analyzed using an MMRM model similar to the primary efficacy analysis ([Section 7.2.3.2.1](#)) with adjusting the corresponding baseline; other continuous variables with one scheduled post-baseline assessment (ie, change in MADRS total score, HAM-A total score, EDE-QM global score and subscale scores) will be analyzed using an ANCOVA model similar to the supportive analysis for the primary efficacy endpoint ([Section 7.2.3.2.3](#)) with adjusting the corresponding baseline as a covariate. The treatment differences and 95% CIs for each dasotraline group relative to placebo in the change from baseline will be obtained from this model.

The proportion of binge eating responders at Week 12 will be analyzed using a logistic regression model and LOCF approach with factors of treatment, pooled center, baseline binge days category (stratification factor), and baseline number of binge episodes per week as covariate. For subjects who are discontinued, binge eating responders at Week 12 LOCF is defined per the last post-baseline time period during the treatment period that binge diary is assessed. To ensure that the logistic regression model is feasible, pooled region may be removed from the analysis model if some pooled center has no responder either because there is a small number of subjects in the pooled center or subjects experience little change (for example, no subject achieving at least 75% reduction in number of binge episodes per week). In addition, for each dasotraline group (vs. Placebo), effect size and the number needed to treat (NNT) will be presented as well. The effect size will be calculated as $\log(\text{odds ratio}) \cdot \sqrt{3}/\pi$, where odds ratio is based on 2 by 2 contingency table and the NNT is derived as $1/\text{Risk Reduction}$, where Risk Reduction (RR) = (each dasotraline response rate – placebo response rate). The 95% CI of NNT will be obtained similarly by using the 95% CI of the RR when both lower and upper confidence limits are positive. The NNT and 95% CI results will be provided in whole number format as any fractional values are rounded up to the nearest whole number (the lower confidence limit is rounded down and the upper confidence limit is rounded up.)

As a supportive analysis, the proportion of binge eating responders for achieving 75% reduction over time will be analyzed, respectively, by an inverse probability weighting (IPW) Generalized Estimating Equations (GEE) model. See [Attachment 9.3.4 \(\[6\]\)](#) for details.

321

In addition, the number and percentage of subjects in the following categories for reduction in the number of binge eating episodes from baseline will be summarized by treatment and by visit:

- cessation (defined as 100% reduction)
- 99% to 75% reduction
- 74% to 50% reduction
- other

At each assessment time point, for each of above continuous secondary efficacy variables, summary statistics (N, mean, standard deviation, median, and range) will be presented for the actual values and the changes from baseline. The 95% CIs of the changes from baseline will also be presented.

Plots of the mean actual values as well as MMRM LS means (\pm SE) of change in number of binge days over time by treatment group will be presented for the ITT and PP populations; plot for ANCOVA LS means (\pm SE) of change will be also presented over time including Week 12 LOCF endpoint. Similar plots of the key secondary endpoints such as BE-CGI-S score, Y-BOCS-BE total score, and number of binge episodes over time will also be provided based on the ITT population.

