5.3. Other Secondary Objectives

The other secondary objectives of the study are:

- To evaluate the efficacy of 2 doses of dasotraline (4 and 6 mg/day) compared with placebo in adults with moderate to severe BED as measured by:
 - Number of binge episodes per week
 - Proportion of binge eating responders at Week 12 who show $\geq 75\%$ reduction in the number of binge eating episodes
 - Sheehan Disability Scale (SDS)
 - Montgomery-Asberg Depression Rating Scale (MADRS)
 - Hamilton Anxiety Rating Scale (HAM-A)
 - Eating Disorder Examination Questionnaire (EDE-Q) modified
- To evaluate the safety and tolerability of 2 doses of dasotraline (4 and 6 mg/day) using physical examinations, 12-lead electrocardiograms (ECG), vital signs, AE reports, clinical laboratory results, body weight, body mass index (BMI), and Columbia – Suicide Severity Rating Scale (C-SSRS)

- To assess potential withdrawal effects upon abrupt discontinuation of dasotraline after 12 weeks of continuous daily treatment using the following assessments (administered during the withdrawal period):
 - Cocaine Selective Severity Assessment (CSSA)
 - Discontinuation-Emergent Signs and Symptoms (DESS) Scale
 - Symptoms of anxiety utilizing the HAM-A
 - Symptoms of depression utilizing the MADRS
- To assess the abuse potential of dasotraline utilizing a comprehensive abuse potential monitoring plan (APMP)
- To assess the relationship between dasotraline plasma concentration and the primary efficacy and selected secondary efficacy and safety endpoints

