10.1.1. Dose or Dosage for Study Drug

Subjects randomized to placebo will receive placebo for the duration of the treatment period.

Subjects randomized to 4 mg/day dasotraline will receive 4 mg/day for the duration of the treatment period.

Subjects randomized to 6 mg/day dasotraline will be dosed with 4 mg/day dasotraline for the first 2 weeks of the treatment period and will be increased to 6 mg/day at Week 2.

No other changes in dose are allowed during the study. Subjects who cannot tolerate the assigned dose at any time in the study will be discontinued.

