15.1. Sample Size

The sample size for this study was estimated based on 2 hypotheses associated with the primary efficacy endpoint (change from baseline in number of binge days per week at Week 12). A fixed sequence closed testing procedure was used to adjust for 2 comparisons of dasotraline doses vs placebo (ie, with dasotraline 6 mg vs placebo tested first and dasotraline 4 mg vs placebo tested after if the previous one is significant at the 0.05 level) for the sample size justification. Based on the Study SEP360-221 results, assuming a common standard deviation (SD) of 1.75 and a mean improvement of 0.9 (effect size 0.517) and 0.8 (effect size 0.457) over placebo for change from baseline in number of binge days per week at Week 12 for dasotraline 6 mg/day and 4 mg/day doses, respectively, a sample size of 96 subjects per treatment group will provide at least 85% conjunctive power to reject both null hypotheses. An upward adjustment of approximately 40% is assumed to compensate for subjects who are randomized but discontinue from the study, thus, a total sample of 480 subjects (160 subjects per group) will be randomized with a ratio of 1:1:1 for placebo, and dasotraline 4 mg/day and 6 mg/day, respectively. The sample size calculation was based on Monte Carlo simulation from EAST 6.4.

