The proportion of binge eating responders at Week 12 will be analyzed using a logistic regression model and LOCF approach with factors of treatment, pooled center, baseline binge days category (stratification factor), and baseline number of binge episodes per week as covariate. For subjects who are discontinued, binge eating responders at Week 12 LOCF is defined per the last post-baseline time period during the treatment period that binge diary is assessed. To ensure that the logistic regression model is feasible, pooled center may be removed from the analysis model if some pooled center has no responder either because of a small number of subjects in the pooled center or subjects experiencing little change. As a supportive analysis, the proportion of binge eating responders over time will be analyzed by an inverse probability weighting (IPW) Generalized Estimating Equations (GEE) model. The details will be provided in the SAP.

In addition, the number and percentage of subjects in the following categories for reduction in the number of binge eating episodes from baseline will be summarized over time by treatment:

- cessation (defined as 100% reduction)
- 99% to 75% reduction
- 74% to 50% reduction
- other

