3.1. Determination of Sample Size

The sample size for this study was estimated based on 2 hypotheses associated with the primary efficacy endpoint (change from baseline in number of binge days per week at Week 12). A fixed sequence closed testing procedure was used to adjust for 2 comparisons of dasotraline doses vs placebo (ie, with dasotraline 6 mg vs placebo tested first and dasotraline 4 mg vs placebo tested after if the previous one is significant at the 0.05 level) for the sample size justification. Based on the Study SEP360-221 results, assuming a common standard deviation (SD) of 1.75 and a mean improvement of 0.9 (effect size 0.517) and 0.8 (effect size 0.457) over placebo for change from baseline in number of binge days per week at Week 12 for dasotraline 6 mg/day and 4 mg/day doses respectively, a sample size of 96 subjects per treatment group will provide at least 85% conjunctive power to reject both null hypotheses. An upward adjustment of approximately 40% is assumed to compensate for subjects who are randomized but discontinued from the study, thus, a total sample of 480 subjects (160 subjects per group) will be randomized with a ratio of 1:1:1 for placebo, and dasotraline 4 mg/day and 6 mg/day. The sample size calculation was based on Monte Carlo simulation from EAST 6.4.

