6.2. Methods of Analysis

6.2.1 General Methodology

All statistical inference analyses will be performed with 2-sided tests at a significance level of 0.05, and 2-sided 95% confidence intervals (CIs) will be calculated whenever appropriate. All

321

data will be summarized by treatment group and visit as appropriate. All subject data will be presented in data listings by subject.

Data for unscheduled assessments will be included when deriving baseline values and the worst case analysis during an assessed period. Unscheduled visits will also be included in treatment endpoint (Week 12 LOCF), which is the last available non-missing treatment endpoint carried forward to Week 12.

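### Week 12 responder status (≥75% fewer binge episodes) can be carried forward from before discontinuation, and no planned analysis of this endpoint, or its NNT, counts leavers as non-responders

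*SAP*

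**What the plan says.** Protocol 5.3 sets the objective as the "Proportion of binge eating responders at Week 12 who show" at least a 75% reduction in binge episodes. Protocol 15.4.1.5 gives the method: "The proportion of binge eating responders at Week 12 will be analyzed using a logistic regression model and LOCF approach". For leavers, SAP 7.2.6.2 repeats the protocol's rule: "For subjects who are discontinued, binge eating responders at Week 12 LOCF is defined per the last post-baseline time period during the treatment period" with an assessed diary.

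The same SAP paragraph adds an NNT for each dasotraline group. It is one over the difference in response rates, rounded up to a whole number, and no separate missing-data rule is given for it. The only other model for this endpoint is a supportive inverse-probability-weighted GEE. A by-visit table of reduction categories is also planned, with no stated denominator and no rule for leavers.

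Two further provisions bear on how many subjects are involved. Protocol 10.1.1 states: "Subjects who cannot tolerate the assigned dose at any time in the study will be discontinued". Protocol 15.1 states: "An upward adjustment of approximately 40% is assumed to compensate for subjects who are randomized but discontinue from the study".

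**The concern.** The objective asks about response at Week 12. For a leaver, the analysis answers a different question: response in the last diary period on treatment, whenever that was. Under Protocol 13.3, a subject who stops drug completes an EOT visit and the three-week withdrawal assessments. Someone who stops at Week 3 is therefore followed to about Week 6, and Week 12 status is never observed.

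Responding early and then leaving is plausible here. Protocol 4.2 reports that the earlier BED study separated from placebo from Week 1, and that decreased appetite and insomnia were among its commonest adverse events. The carried value can also rest on few days. SAP 5.1.1.1 and 5.1.1.2 scale whatever non-missing diary days exist to a weekly rate, and I find no minimum number of days in the supplied text.

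At stake is how the response difference and NNT are read. A reader may take a Week 12 NNT to describe benefit still present at Week 12, when part of it may come from subjects who had already stopped.

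**Working it through.** **The plan's own figure.** Inputs from SAP 3.1 and 6.2.1: "assuming a common standard deviation (SD) of 1.75 and a mean improvement of 0.9 (effect size 0.517) and 0.8 (effect size 0.457) over placebo"; "a sample size of 96 subjects per treatment group will provide at least 85% conjunctive power to reject both null hypotheses"; "All statistical inference analyses will be performed with 2-sided tests at a significance level of 0.05".

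- SE of a difference = 1.75 × √(2/96) = 0.2526.
- Power for 6 mg: Φ(0.9/0.2526 − 1.96) = 0.946. Power for 4 mg: Φ(0.8/0.2526 − 1.96) = 0.886.
- Conjunctive power, with correlation 0.5 from the shared placebo arm, is 0.854 (0.853 by simulation with t tests). The stated 85% is reproduced. The ratio 0.9/1.75 is 0.514 rather than 0.517, which has a negligible effect.
- 96/(1 − 0.40) = 160, whereas 96 × 1.4 = 134.4. The 160 per group therefore corresponds to 40% of randomised subjects discontinuing, and 0.40 × 160 = 64 per arm.

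**How the two methods differ.** In each arm let d be the proportion leaving, c the response rate among completers, and l the response rate among leavers in their last period.

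- LOCF rate = (1 − d)c + d·l
- Leavers as non-responders = (1 − d)c
- Gap between the two treatment differences = d(drug)·l(drug) − d(placebo)·l(placebo)

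**Illustration.** The documents give no response rates and no dropout by arm, so every value of c, l and arm-specific d below is an assumption.

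- Set A: completers 60% drug, 35% placebo; leavers 45%, 25%.
- Set B: completers 65% drug, 40% placebo; leavers 25%, 15%.

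NNT is rounded up, as the SAP specifies.

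| Set | Dropout, drug / placebo | LOCF rates | Difference (NNT) | Leavers as non-responders | Difference (NNT) | Gap, points |
|---|---|---|---|---|---|---|
| A | 40 / 40 | 54.0 v 31.0 | 23.0 (5) | 36.0 v 21.0 | 15.0 (7) | 8.0 |
| A | 45 / 35 | 53.25 v 31.5 | 21.75 (5) | 33.0 v 22.75 | 10.25 (10) | 11.5 |
| A | 20 / 20 | 57.0 v 33.0 | 24.0 (5) | 48.0 v 28.0 | 20.0 (5) | 4.0 |
| A | 25 / 45 | 56.25 v 30.5 | 25.75 (4) | 45.0 v 19.25 | 25.75 (4) | 0 |
| A | 20 / 45 | 57.0 v 30.5 | 26.5 (4) | 48.0 v 19.25 | 28.75 (4) | −2.25 |
| B | 40 / 40 | 49.0 v 30.0 | 19.0 (6) | 39.0 v 24.0 | 15.0 (7) | 4.0 |
| B | 40 / 20 | 49.0 v 35.0 | 14.0 (8) | 39.0 v 32.0 | 7.0 (15) | 7.0 |
| B | 20 / 20 | 57.0 v 35.0 | 22.0 (5) | 52.0 v 32.0 | 20.0 (5) | 2.0 |
| B | 20 / 40 | 57.0 v 30.0 | 27.0 (4) | 52.0 v 24.0 | 28.0 (4) | −1.0 |

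Worked line, A at 40/40: LOCF drug = 0.6 × 0.60 + 0.4 × 0.45 = 0.54; placebo = 0.6 × 0.35 + 0.4 × 0.25 = 0.31. The gap is 0.18 − 0.10 = 0.08.

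The gap is zero when placebo dropout is l(drug)/l(placebo) times drug dropout. That ratio is 0.45/0.25 = 1.8 in set A and 0.25/0.15 = 1.67 in set B. Above it, the sign reverses.

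**The case against.** **Direction.** A reader might infer that LOCF must flatter the drug, or that the gap disappears only when both arms leave and respond equally. The formula supports neither. Protocol 13.1 lists lack of efficacy among the reasons for stopping, and this could raise placebo dropout. This part of the objection stands in full.

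**Who is counted.** A reader might also infer that every early leaver becomes a responder. Only those whose last assessed period reached a 75% reduction do; the other leavers remain non-responders.

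**Transparency.** The plan does not hide the method. SAP 6.1.3.1, 6.2.1 and 7.2.6.2 define and label the endpoint as Week 12 LOCF, so no relabelling is needed.

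**Existing safeguards.** The by-visit category table may allow an observed Week 12 responder count to be read off, but its denominator is unstated. Under SAP Table 5, early-termination diaries after Week 10 map to Week 12. The 4-week cessation endpoint (SAP 5.1.1.4) counts a subject as a failure for leaving before 28 diary days or for missing diary in the last 28. That is a different endpoint, and a leaver with 28 clean days can still succeed on it. Binge episodes per week at Week 12 are analysed by MMRM. The weighted GEE, as named, reweights subjects still observed; its details are in Attachment 9.3.4, which was not available. None of these gives a model-based responder comparison or an NNT with leaving as failure.

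**Choice of question.** A Week 12 endpoint does not by itself say that stopping is failure. Non-response is one legitimate strategy, which is why it belongs beside LOCF rather than in its place.

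**Conclusion.** The gap in the plan is real but limited. For the ≥75% responder endpoint, carried-forward status can decide Week 12 response for up to about 64 of 160 subjects per arm if the planned-for discontinuation occurs. No planned analysis shows the result with leavers as non-responders. That the NNT uses LOCF rates is inferred from its position in the paragraph; the SAP does not state it.

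Relative to counting leavers as non-responders, LOCF overstates the difference and understates the NNT when dropout times leaver response is larger on drug. Across the assumed scenarios the gap runs from −2.25 to +11.5 points. The largest NNT change is 8 to 15, and several scenarios show none. These figures show sensitivity to assumptions and do not predict this trial.

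A reader might extend the point to the trial's main claims. The documents do not support that: this endpoint is outside the fixed sequence, which covers only the primary and key secondary endpoints.

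**What to change.** Keep the LOCF analysis. In SAP 7.2.6.2 add a sensitivity analysis, prespecified before unblinding, using the same logistic model. In it, a subject without diary data for the scheduled Week 12 visit period is a non-responder. State that an early-termination diary mapped to Week 12 under SAP Table 5 does not qualify. Report the NNT and its CI from this analysis beside the LOCF ones, under the SAP's existing rounding and CI rules. State explicitly which response rates feed each NNT.

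The cost is a few lines of SAP text and one extra model run, with no new data. The reported difference and NNT may look less favourable. Subjects who miss Week 12 for reasons unrelated to treatment will also count as non-responders, so the two results should be read together.
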